The VA Pharmacy Benefits Management Services uses several tools to encourage optimal use of medications including: 1) National Formulary, 2) Prior Authorization, 3) Criteria for Use, and 4) VA Center for Medication Safety. ADT is currently listed on the VA National Formulary as a standard pharmacy benefit to eligible patients. No prior authorization is necessary to ensure ADT use is appropriate. For this pilot, we plan to test implementation of a CPRS order check at the facility level. An order check was selected because it will flag prescribers that ADT may not be guideline supported for the Veteran, but it will not be a hard stop – providers can move through the order restriction to order ADT without additional delays upon entering the indication (or any text) into a text field. To reduce burden on providers as much as possible, this flag will only be triggered for Veterans with localized prostate cancer getting primary ADT or Veterans getting ADT for non-metastatic biochemical recurrence with a low PSA level. We note that this approach makes this a benign intervention: providers are not required to cross administrative hurdles to be able to order ADT if they feel they have good reason to do so.

C2.1.2 Tailoring a formulary restriction strategy for ADT de-implementation

Our formulary restriction intervention involves a refined version of the current EMR order check template developed and in use by [name] and [name] (Co-PI) at the VA Ann Arbor to limit inappropriate prostate cancer screening.⁷¹ In general, these templates vary widely across the system, can be made more or less extensive, and can build in limited forms of decision support to specialists prescribing ADT. This is a very flexible, widely used approach, for which the technology already exists and is integrated into the EMR.

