We used the taxonomy outlined by Wright et al.⁸⁴ to describe the decision support content and the Template for Intervention Description and Replication (TIDieR) checklist guided the refinement and tailoring.⁸⁵ For example, when an ADT injection is ordered, a brief interruptive message *tailored* to our prioritized barriers TDF themes and behavior change techniques (e.g., *persuasion, training, education*) based on our prior work, will be shown on the ordering screen. This will allow the provider the option of proceeding or cancelling the order, with or without justification. To ensure this formulary restriction approach is 'smart' we will use the following criteria as we begin and explore options during refinement: 1) injectable ADT order in pharmacy claims (e.g., leuprolide J9217), 2) prostate cancer diagnosis (ICD-9 185, ICD-10 C61), and 3) low PSA level (e.g., levels <2 ng/mL are consistent with non-metastatic disease⁴). We will continue to refine these criteria throughout the pilot with the investigative team. We will vary alert criteria (e.g., prior ADT injection, PSA level) to ensure the number of triggers are acceptable to providers as done previously. We will pilot our theory-based messaging, presentation, and approach, at the VA Ann Arbor Healthcare System, VA Greater Los Angeles Healthcare System, and VA NY Harbor Healthcare System, with ongoing refinement. These pilot sites have been selected because we have study team member presence to help facilitate implementation and assessment.

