All 3 pilot test sites will be followed for up to 6 months. To implement the interventions and assess for issues in the implementation process in order to further refine the intervention plan, information will be collected regarding the process of ADT ordering at each site, including who is involved, through conversations with the Site Champion (who is also a project consultant) or their designee. Additionally, information regarding implementation status as well as any changes in site processes around prescribing ADT will be discussed at regular team meetings with the project consultants (including Site Champions). For both the pilot and implementation trial, outcomes will be collected from VA CDW/Cancer Registry/Vital Status/CMS records and CPRS/Capri/JLV/WebVRAM for all clinic visits documented as providing low-value ADT at baseline, 3 and 6 months. An organizational survey will be developed and refined throughout the pilot. For the pilot implementation trial, an anonymous clinic assessment survey will be administered to Site Champions at baseline and an ADT provider assessment will be administered to participating site providers at baseline and 1-month post-intervention through VA Qualtrics (Appendix VI).

Outcomes Analyses

Primary analyses: Comparing the effectiveness of two de-implementation strategies, **Or** vs. **Sc**, on continued low-value ADT use after six months. Our primary outcome is stopping ADT injections, which will likely be evaluated through a combination of chart reviews and informatics data generated through the ordering process. We will also explore the feasibility and impact of six-month outcomes during pilot testing to increase study efficiency and timeliness.

Secondary outcomes: RE-AIM implementation outcomes, changes from baseline measures, total ADT injections per arm at 6 months post implementation. (Table 4). We will examine moderators of strategy effectiveness (e.g., fidelity) and causal mechanisms underlying the strategies through content analysis from study team and pilot site meeting documents and discussion and based on our organizational assessment.

Table 4. Implementation Outcomes (based on the RE-AIM framework)

Domain	Order entry	Script
Reach	$(1 - \# \text{ ADT providers opt out}) / (\text{total ADT providers})$	$(1 - \# \text{ ADT provider opt out}) / (\text{total ADT providers})$

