Effectiveness *** (primary implementation outcome, and primary outcome of trial)	Low value ADT (LVADT) prescription order decrease $(\text{LVADT candidate expected orders} - \text{LVADT not ordered}) / (\text{LVADT got order} + \text{LVADT stopped order})$	
Adoption (provider level)	At least 1 order fired and signed (provider level)	At least 1 script signed (provider level)
Penetration Adoption (order level)	$(\# \text{ times order entry justified}) / (\# \text{ times order went through anyway})$	$\# \text{ scripts signed} / (\text{LVADT got order} + \text{LVADT stopped order})$
Implementation	Did implementation vary? 
- Differential adoption/penetration in medical oncology vs radiation oncology vs urology- Measure adoption/penetration at different time points (e.g., 3/6 months)- Number of sites that withdraw from participation (e.g., 3/6 month withdrawal rates)	
Fidelity	
- Were the justifications appropriate? (i.e., was something entered, or was no reasoning put in (enter n/a, etc))	
- Was the script edited? (i.e., not just signed)
Maintenance (site/setting level)	Proportion of sites that would elect to continue intervention, if available	

TIMELINE

R37 Funding: 1/1/2022 – 12/31/2023

PILOT SITE SELECTION

- The **Or** and **Sc** interventions will be piloted at the study PI and consultants' sites as follows:

Site	Site Champions	Intervention
VA Ann Arbor Healthcare System	[name] (co-PI)	Or & Sc
VA Greater Los Angeles Healthcare System	[name]	Or
VA New York Harbor Healthcare System	[name]	Or

PILOT SITE IMPLEMENTATION OVERVIEW

- Drs. [name], [name], and [name] are all consultants who have agreed to serve as Site Champions for the pilot work.
 - Study consultants do not have access to identifiable data or the study folder and are not "engaged" in study activities.
- Pilot sites will not be randomized.
- The ADT Order Check Attestation Intervention (**Or**) will be implemented at all sites, as this intervention requires engagement with other services, such as CAC, pharmacy, etc., and its procedures are most in need of refinement.
- The ADT Provider Script Intervention (**Sc**) will be implemented at Ann Arbor.
- The official start date for the pilot begins when we have started adding HF's and/or assigning progress notes. Pilot sites will be followed for up to 6 months.
- Facility Notifications & Approvals

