- Once the CROC has been switched to live mode, study staff will place a "Living Well ADT" health factor in the EMR of patients whose clinic visits study staff have confirmed to be targets for ADT de-implementation. We will enter health factors as we identify eligible patients. This health factor combined with a low PSA level (most recent PSA < 2ng/mL) will trigger the ADT Order Check Attestation Intervention (**Or**) when the provider places an order for ADT (Lupron, Eligard, Viadur, Goserilin, and Zolodex).
- Providers may override the CROC by entering a number from the order check text that corresponds to the reason they are overriding the order check. Providers are also able to enter text if a numbered reason is not listed.
- If providers opt-out after the health factor was placed for one of their patients, study staff will remove the health factor in CPRS. For a provider who opts-out, the Study Data Manager will run a query in our Access tracking database to pull a list of his/her patients. The Study Team will not place a health factor in the EMR of patients whose provider has opted out.
- Study staff will do periodic quality control checks to ensure the intervention is working as expected and work with the site CAC's to make adjustments as necessary.
- Appropriate use of the indication will be tracked for fidelity. We will track comments entered by providers to override order checks. The Study Data Manager will periodically pull comments from order checks (there are data tables for order checks that contain text for open field that are stored in CDW).
 - Using a combination of progress notes and other CPRS data, study staff will check to determine whether the patient received the injection.
- Deimplementing Or – study staff will remove HFs for intervention patients. We'll ask site to remove study HF from their CPRS.

CPRS INSTRUCTIONS FOR OR INTERVENTION

OPENING CPRS

- Go to "VA Shortcuts" (star icon on desktop)
- Select "CPRS _Launcher" (rocket icon)
- Select: VISN 03 or VISN 22
- Select site: Ex - Manhattan, NY
- Launch CPRS button

PLACING A HEALTH FACTOR

While in a patient record in CPRS:

- Click on the "Notes" tab (bottom of screen)

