(1 of 2) Duplicate Therapy: Order(s) exist for {LEUPROLIDE (ELIGARD) 22.5MG(3 MONTH) LA INJ [PENDING]} in the same therapeutic categor(ies): LHrH(GNrH) Agonist Analog Pituitary Suppressants, Precocious Puberty Agents

(2 of 2) ADT Advisory - Living Well
This patient has a PSA < 2 and does not appear to have metastatic prostate cancer based on multidisciplinary review.

For this clinical scenario, where the harms of ADT likely outweigh the benefits, NCCN (tinyurl.com/2p9f5w8r) and AUA (tinyurl.com/4ueptrtd) guidelines recommend either transitioning to intermittent ADT or discontinuation of ADT.

Instead of ADT now, consider patient reassurance with return visit in 3 months for a PSA test and symptom assessment.

Please enter reasons for overriding order checks as free text or a number from the list below:

- 10. Provider recommendation: Local Symptoms OR Asymptomatic, high-risk/very high-risk, N0/M0 with less than 5 year life expectancy.
- 20. Provider recommendation: Rapidly rising PSA/short PSA-DT (<10 months)
- 30. Provider recommendation: Metastatic or presumed metastatic disease
- 40. Provider recommendation: Castration resistant prostate cancer
- 50. Patient Preference/anxiety (consider reassurance with return visit in 3 months for PSA check)

Accept Order Cancel Order Drug Interaction Monograph

PROVIDER SCRIPT (Sc) INTERVENTION

- The pilot work will be used to refine the Provider Script Intervention for use in the cRCT, as needed.
- The purpose of the script is to enable providers to:
 - Improve interpersonal skills
 - Increase confidence in the evidence base and communication surrounding low-value care
- It is up to the discretion of the provider whether/how to incorporate the script into the clinic visit discussion.

PROGRESS NOTE

- We will work with [name] ([contact]), or another, AAVA CAC, to develop the progress note template. We will also create an instruction guide for CACs at other sites to upload the note template file in CPRS.
- [name], or another AAVA CAC will send the note template via VISTA email to local CACs with directions to install. In the event [name] is not available, [name] ([contact]), or [name] ([contact]) can send the VISTA file if we provide them with the local CAC's VISTA email.
- This is the exact entry for the reminder dialog they would need unless we make any updates to it between now and then.

+Item	Entry	Source	Date Packed
181	LIVING WELL ADT FILES - DEC 2022	[name]	12/13/2022@10:12

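### Table 4 prints Reach as one minus a count, divided by the total, so it is not a participation proportion; the two order-level penetration ratios beside it also need labels saying they have different bases

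*Protocol*

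**What the plan says.** The Protocol's Outcomes Analyses section names the RE-AIM implementation outcomes as secondary outcomes and defines them in Table 4, with one column for the order check (Or) and one for the script (Sc).

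- **Reach**, Or column: "1 - \# \text{ ADT providers opt out}) / (\text{total ADT providers". The Sc column has the same form.
- **Order-level penetration**, Or column: "times order entry justified}) / (\# \text{ times order went through anyway".
- **Order-level penetration**, Sc column: "scripts signed} / (\text{LVADT got order} + \text{LVADT stopped order".

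Opting out is an individual act: under Intervention Kick-Off, each provider has a week to opt out by email. The opt-out term in Reach is therefore a count of people.

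Three places describe how an order passes the check. Section C2.1.1 says "providers can move through the order restriction to order ADT without additional delays upon entering the indication (or any text) into a text field". The Or intervention section says "Providers may override the CROC by entering a number from the order check text that corresponds to the reason they are overriding". Section C2.1.2 says "This will allow the provider the option of proceeding or cancelling the order, with or without justification". The order-check screen also lets the provider cancel (its buttons read "Accept Order Cancel Order Drug Interaction Monograph").

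Pilot Data Collection and Trial Data Collection promise that ascertainment and analysis will be refined during the pilot. Neither gives a replacement formula.

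**The concern.** Reach should be the share of ADT providers who did not opt out, a number between 0 and 1. The printed expression lies outside that range once two providers opt out. With full participation it gives a value close to zero. A named secondary outcome cannot be reported from the formula as it stands.

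The penetration row raises a lesser question. Its two cells share one label but use different denominators. A flagged order that the provider cancels drops out of the Or ratio altogether, whereas stopped orders stay in the Sc denominator. A reader who sees the two values side by side may take them as the same quantity measured in two arms. The Implementation row reuses penetration by specialty and at 3 and 6 months, so the label carries forward.

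**Working it through.** **Inputs.** The formulas come from Table 4. The Protocol gives no number of ADT providers, opt-outs or low-value orders, so the counts below are assumptions for illustration. Table 4 states no numerical value of Reach or penetration to reproduce.

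**Reach.** Let N be the total ADT providers and k the number opting out.

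- As printed: (1 - k)/N
- Evidently intended: 1 - k/N = (N - k)/N
- Gap: (N - k)/N - (1 - k)/N = (N - 1)/N, which does not depend on k. The two forms agree only if N = 1.

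| N (assumed) | k | Printed (1 - k)/N | Intended 1 - k/N |
|---|---|---|---|
| 10 | 0 | 0.10 | 1.00 |
| 10 | 1 | 0.00 | 0.90 |
| 10 | 2 | -0.10 | 0.80 |
| 10 | 5 | -0.40 | 0.50 |
| 20 | 0 | 0.05 | 1.00 |
| 20 | 1 | 0.00 | 0.95 |
| 20 | 2 | -0.05 | 0.90 |
| 20 | 5 | -0.20 | 0.75 |
| 40 | 0 | 0.025 | 1.00 |
| 40 | 1 | 0.00 | 0.975 |
| 40 | 2 | -0.025 | 0.95 |
| 40 | 5 | -0.10 | 0.875 |

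The printed value is too low by (N - 1)/N: 0.90, 0.95 and 0.975 for N = 10, 20 and 40. Because this shift depends on N, two groups with full participation but different numbers of providers would show different Reach: 0.10 for N = 10 and 0.05 for N = 20, where both should be 1.00.

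**Penetration bases.** Assume 100 low-value order opportunities, s of them stopped, and a share q of the orders that proceed carrying a justification.

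- Or as printed: q(100 - s)/(100 - s) = q, undefined if s = 100
- The same numerator over the Sc denominator: q(100 - s)/100

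| Stopped s | q | Or as printed | Over given + stopped |
|---|---|---|---|
| 0 | 1.0 | 1.00 | 1.00 |
| 10 | 1.0 | 1.00 | 0.90 |
| 30 | 1.0 | 1.00 | 0.70 |
| 50 | 1.0 | 1.00 | 0.50 |
| 30 | 0.8 | 0.80 | 0.56 |

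The printed Or ratio simply returns the assumed q. The table therefore says nothing about the value the trial will see. It shows only that the two bases coincide when no order is stopped and separate as more are stopped.

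**The case against.** **Reach is a typographical slip.** The intended form is obvious, and an analyst holding a provider list and an opt-out count would not publish a negative proportion. That is fair as to consequence. The text was also machine-read from PDF, so the bracket should be checked against the source, although its appearance in both columns makes a reading fault unlikely. The objection does not supply a correct definition, and the Protocol has none elsewhere.

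**The measures are provisional.** The Protocol does promise refinement. However, the text carries a Version 6 footer dated 10/04/2023 and already contains note-assignment instructions for randomized-trial sites, so Table 4 is the definition in force.

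**Arm-specific penetration formulas are legitimate.** This largely stands. The tools act at different moments, Adoption and Fidelity are also arm-specific, and the share of proceeding orders that were justified is a coherent question. Stopped orders are not lost, since the Effectiveness row counts them. Only the shared label remains at issue.

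A reader might infer more from the penetration row than the Protocol supports:

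- *That an Or-versus-Sc comparison is biased.* No such test of penetration is planned, and the stated reuse by specialty and time point can be done within each arm.
- *That the Or ratio must sit near 1 because text is required to proceed.* Section C2.1.2 allows proceeding without justification, and the Fidelity row treats an entry such as n/a as no reasoning, so a substantive reading of justified is open.
- *That Sc penetration has a built-in ceiling because injection-only visits receive no note.* Table 4 does not say that orders at such visits enter the denominator, and the Protocol gives no count of them.

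**Conclusion.** The Reach formula is wrong as written in both columns. It falls short of the participation proportion by (N - 1)/N, for example 0.95 with an assumed 20 providers, and is negative from two opt-outs onward. That algebra needs no assumption; only the illustrative N and k are assumed.

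The penetration formulas are not errors. They have different bases under one label, and the Or ratio overlaps the Fidelity item on whether a reason was entered. This is a minor matter of labelling and interpretation.

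The primary outcome, power and alpha are unaffected. A reader might go further and conclude that Or penetration must be rebuilt, for instance as checks fired over orders given plus stopped. The Protocol does not compel that. Such a measure would still not vary with cancellations, would record exposure rather than provider action, and would need firing records that the Or section does not describe retrieving.

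**What to change.** 1. In Table 4, both columns, state Reach = 1 - (opted-out ADT providers / total ADT providers).
2. In the penetration row, label the Or ratio as an attestation measure among overridden orders. Add one sentence saying that it excludes cancelled orders, that Sc penetration is taken over orders given plus orders stopped, and that the two figures are not to be compared across arms.

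The first change moves one bracket and the second adds a label and a footnote. Neither requires new data, and neither touches the primary analysis.

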 1. Never had evidence of metastatic disease (including bones and lymph nodes)
 2. No treatment with CRPC medications (e.g., abiraterone, enzalutamide) in the last two years
 3. Has completed definitive treatment with radiation (+/- adjuvant ADT), RP, or cryotherapy
 4. Receiving ongoing ADT at the VA
 5. No rise in PSA level after definitive treatment
 - Current PSA ≤2 and not rapidly rising (no PSADT <10 months)

- Throughout the pilot, the data manager will complete data pulls at different time intervals (e.g., weekly, bi-weekly, monthly, etc.) to determine how often the data may need to be refreshed during the RCT. Data such as patient appointment cancellations, changes in PSA scores, new drug names, variations of appointments/treatments, etc. are important to keep updated as they can impact patient eligibility.

MPCA NATURAL LANGUAGE PROCESSING (NLP) TOOL USE IN VINCI

- We will use a validated NLP tool developed by the VA Salt Lake City Healthcare System Prostate Core to identify Veterans with metastatic prostate cancer (mPCa) in real time. This will enable us to further refine our cohort by excluding all mPCa patients.
 - The Prostate Core has provided a data dictionary for definitions of the variables.
 - We will inform the Prostate Core if any of our definitions are different (e.g., prostate cancer, mPCa, etc.).
 - In the event we find mPCa patients after we complete chart reviews, we will inform the Prostate Core team.
 - Study staff will view the NLP data output in a VINCI worksheet.

- The PCa Data Core table/list is updated monthly by VINCI (we should receive email notifications from VINCI when the list has been updated).

CHART REVIEWS

- Study staff will also **conduct chart reviews using CPRS/Capri/JLV/WebVRAM to confirm target ADT orders and clinic visits.**
 - Study staff will apply for local CPRS access at participating sites through WebVRAM, though Capri/JLV may also be used to conduct chart reviews

- As the ADT injections occur serially at 1, 3, or 6 month intervals, an individual provider could have multiple opportunities to be exposed to the intervention during the 6-month study period.

- Low-value ADT injections must have occurred within 14 months prior to data pull.

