- If requested by sites, the study will provide supplies to sites to display the clinic handouts. Study staff will check in to ensure handouts were received and are being displayed and/or made accessible to providers and to address any issues that come up.
- It is up to the discretion of the provider whether/how to incorporate the handout into the clinic visit discussion.

CPRS INSTRUCTIONS FOR Sc INTERVENTION

ASSIGNING A PROGRESS NOTE

1. Open TWO files:
 - a. CPRS
 - b. *Database
 - i. Note: Starting 8/10, [name] will assign progress notes for Columbia and Phoenix patients.
 - ii. Note: Starting 8/14, [name] will update the appointment list for eligible patients each week (on Mondays). The database will list dates of upcoming appointments in chronological order.
2. While in a patient record in CPRS:
 - a. Confirm patient name and SSN match what's in the database (you're just confirming that you're looking at the correct person in CPRS).
 - b. In CPRS, go to "Appointments" in the "Cover Sheet" to confirm that the appointment listed in the database matches what's listed in CPRS.
 - i. If the date and/or name of an upcoming appointment in CPRS is different than what is in the database, update the "Visit datetime" and "Clinic" name in the database.
- c. In CPRS, confirm the MOST RECENT PSA has not increased beyond 2ng/ml.
 - i. **IF** the patient has a PSA <2ng/ml, skip to Step 2d.
 - ii. **IF** the patient has a PSA >2ng/ml, go back to the database, open the form for the patient, click "View/Edit Chart Reviews" and edit the Patient Chart Review page:
 - 1) HF/Note Comments – add reason for not assigning progress note (i.e., why patient is ineligible) – comment should read as: "Prior to assigning note, it was confirmed the patient's most recent PSA on [DATE] was [PSA value]."
 - 2) Not Elig. At Visit box – check this box
 - 3) Exclusions – select "Yes" next to "Current PSA >2 or rapidly rising"
 - 4) Inclusions – mark all three inclusions "No"
 - 5) Notes – add reason for not assigning progress note (yes, you will repeat step 2.c.i.1) – comment should read as: "Prior to assigning note, it was confirmed the patient's most recent PSA on [DATE] was [PSA value]."
 - 6) Outcomes – mark "Not Eligible"
 - 7) Click "Save"
 - iii. Note: If the patient is ineligible for another reason (i.e., patient is deceased, provider opted out, etc.) follow steps 1)-7) to update this page. The details should be relevant to the specific situation.

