For this clinical scenario, where the harms of ADT likely outweigh the benefits, NCCN (tinyurl.com/2p9f5w8r) and AUA guidelines (tinyurl.com/4ueptrtd) recommend either transitioning to intermittent ADT or discontinuation of ADT.

Talking Points:

-We are learning more about prostate cancer all the time, and continue to update recommendations based on new information. Since hormone therapy comes with long-term effects on your health, I'm worried the harms are greater than the benefit.

-Hormone treatment can have long-term effects that you don't notice right away, like thinning bones, diabetes, and heart disease. Most patients don't notice these conditions until they have a complication like a broken hip.

-If we get any indication that your prostate cancer is behaving more aggressively or causing you problems, we may decide the benefits of hormone therapy are greater than the harms. We can restart the hormone therapy at any point.

Patient information sheet - "Living Well with Prostate Cancer: Is Hormone Therapy Still Right for You?"

tinyurl.com/bdh45bnn

Patient prefers to:
Continue ADT

OR

Discontinue ADT and follow up in 3-6 months with a PSA test

PILOT CLINIC AND ADT PROVIDER ASSESSMENTS

- For the pilot, we will ask the Site Champions/Study Consultants to test the assessment surveys and provide feedback to help refine the survey and implementation procedures for the cRCT.

PILOT DATA COLLECTION

- Feedback from Site Champions/Study Consultants regarding pilot site implementation will be collected informally during study meetings.
- The organizational assessment survey will be fielded to Site Champions/Study Consultants and refined throughout the pilot.
 - Outcome measures in Table 4 will be assessed and approaches to ascertainment, tracking, and analyses refined during the pilots.
- Outcomes will be collected from VA CDW/Cancer Registry/Vital Status/CMS records and CPRS/Capri/JLV/WebVRAM for all clinic visits documented as providing low-value ADT at baseline, 3 and 6 months.

INSTRUCTIONS FOR PHONE FORWARDING AND VOICEMAIL

Study Contact Information is the designated study phone in [name]'s office: [contact].

Phone Forwarding

The instructions for forwarding will depend on the phone, but for the ones currently in the office:

- 1) Select a line and press **FORWARD ALL**
- 2) Dial the number that you want to forward to

[figure not shown]
To deactivate, press **FORWARD OFF**

Checking Study Voicemail

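### Table 4's only formula for the primary outcome, read with a minus sign, gives the share of low-value ADT orders that continued, although it is labelled a decrease.

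*Protocol*

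**What the plan says.** The Effectiveness row of Table 4 (Implementation Outcomes) is marked as the primary outcome of the trial. One formula serves both arms: "Low value ADT (LVADT) prescription order decrease $(\text{LVADT candidate expected orders} - \text{LVADT not ordered}) / (\text{LVADT got order} + \text{LVADT stopped order" (the closing brackets follow). The protocol gives no other formula for this outcome, and it does not define the four terms.

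Two other cells of the table bear on how to read it. The Script entry for order-level penetration has the same denominator: "scripts signed} / (\text{LVADT got order} + \text{LVADT stopped order". The Reach entry uses the same mark as a subtraction: "1 - \# \text{ ADT providers opt out}) / (\text{total ADT providers".

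The prose gives two directions. Under Outcomes Analyses, the primary-analysis paragraph compares the strategies "on continued low-value ADT use after six months". Its next sentence states: "Our primary outcome is stopping ADT injections". Aim 1, under Study Design, speaks of a reduction in low-value use at six months.

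**The concern.** A quantity called a decrease, and meant to capture stopping, should rise as more orders are stopped. In the printed ratio, orders not placed are subtracted in the numerator, so the value falls as they increase.

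The trial is meant to show which of two strategies reduces low-value ADT more. If an analyst applies the formula and reports the result under its label, the arm that stops fewer orders shows the larger decrease. A site that stops nothing shows a decrease of 100%.

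**Working it through.** **Inputs.** All terms come from Table 4: E = candidate expected orders, N = not ordered, G = got order, S = stopped order. The protocol states no value for the outcome, so there is no figure to reproduce. The counts below are illustrative.

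**Printed formula, with a minus sign:** f = (E − N)/(G + S).

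**Natural reading (an assumption, because the terms are undefined):** every expected order is placed or stopped, so E = G + S; the orders not placed are the stopped ones, so N = S. Then

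f = (G + S − S)/(G + S) = G/(G + S) = 1 − S/(G + S).

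With E = 100:

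| Stopped S | Got G | Printed formula (100 − S)/100 | Share stopped S/100 |
|---|---|---|---|
| 0 | 100 | 1.00 | 0 |
| 20 | 80 | 0.80 | 0.20 |
| 40 | 60 | 0.60 | 0.40 |

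Each row sums to 1, so the printed value is the complement of the share stopped.

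**Effect on the arm comparison.** Suppose one arm stops 30 of 100 orders and the other 10 of 100.

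- Share stopped: 0.30 − 0.10 = +0.20.
- Printed formula: 0.70 − 0.90 = −0.20.

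The size is the same and the sign is opposite.

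**Dash reading.** If the mark means *expected orders, not ordered*, the numerator is simply the expected orders that were not placed. On the same assumptions this is S, and the ratio is S/(G + S). With S = 20 it gives 20/100 = 0.20, which agrees with the label.

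**The case against.** **The mark may be a dash.** On that reading the cell is correct, and text taken from a PDF cannot settle the matter. The Reach cell uses the mark as a subtraction, which favours a minus sign. But Reach is itself loose: taken literally, 5 opt-outs among 20 providers gives (1 − 5)/20 = −0.2. The table may be shorthand, and this caveat stands. A primary-outcome formula that can be read as its own complement still needs rewriting.

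**A continuation share matches one sentence of the protocol.** The comparison is also worded as continued use, so one could say that the label is wrong and the ratio right. This stands in part: the passages disagree on direction. But the label, the sentence naming the outcome and Aim 1 all point to stopping or reduction.

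**The table is provisional.** Pilot Data Collection says: "Outcome measures in Table 4 will be assessed and approaches to ascertainment, tracking, and analyses refined during the pilots". Trial Data Collection likewise leaves the outcomes analysis plan to be developed further during the pilot. The present text is Version 6, dated 10/04/2023. Its note-assignment instructions already name two randomized-trial sites, and the formula is still printed. Defining the four terms may properly be left to a statistical analysis plan, so their absence is not the point. The point is that a stated formula contradicts its label.

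**Stronger readings that the documents do not support.** A reader might infer that the formula fails on every reading. It does not, because the dash reading gives the share stopped. A reader might also infer that it is fixed at 1.00 and cannot separate the arms. That needs *not ordered* and *stopped* to be separate groups, which the protocol nowhere says.

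**Conclusion.** The concern holds in a limited form. With a minus sign, E = G + S and N = S, the only formula for the primary outcome equals the share of orders continued, while its label calls it a decrease. For 0, 20 and 40 stopped out of 100, it returns 1.00, 0.80 and 0.60 in place of 0, 0.20 and 0.40.

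Under the label, the sign and meaning of the arm difference are reversed. A reader might infer that the estimated effect would also be wrong in size, or that the trial must name the wrong arm. Neither follows: both arms use the same formula, the size is unchanged, and a wrong conclusion requires the value to be reported as a decrease without anyone noticing.

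Because the row is the trial's primary outcome, the formula should be corrected before it is used. No sample size, power or error rate is involved.

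**What to change.** 1. In the Effectiveness cell, print: LVADT stopped order / (LVADT got order + LVADT stopped order). This reuses the denominator in the Script penetration cell and matches the stated outcome of stopping injections.
2. In the primary-analysis paragraph of Outcomes Analyses, word the comparison in the same direction, as stopping rather than continued use.

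Keeping the ratio and relabelling it as continuation would mend the cell, but it would leave the row pointing the opposite way from the outcome sentence and Aim 1.

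Do not add a rule that excludes due orders lost through cancelled visits or lost eligibility. The protocol recognises such events: "Data such as patient appointment cancellations, changes in PSA scores" are to be kept up to date because they can affect eligibility, and the note-assignment steps cover other losses ("If the patient is ineligible for another reason (i.e., patient is deceased, provider opted out, etc"). But an injection visit may be cancelled because the provider has stopped ADT, so a post-randomization exclusion could remove true stops. At most, report due orders unplaced for other reasons separately by arm.

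The cost is one formula and a few words in one sentence. The outcome, time point, data collection and design do not change.
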